#### Informed Consent:

- Full written informed consent will be obtained for all subjects enrolled in the study.
- Surrogate consent may be obtained if subject is unable to consent due to cognitive impairment, lack of capacity, or serious or life-threatening diseases and conditions of the research subject.
- In an emergency room setting, the order of priority does not apply, nor does the surrogate have to show reasonable knowledge of the subject. Surrogate consent may be obtained from a surrogate decision maker who is any of the following:
  - The person's agent designated by an advance health care directive.
  - The conservator or guardian of the person having the authority to make health care decisions for the person.
  - The spouse of the person.
  - The domestic partner of the person as defined in Section 297 of the Family Code.
  - An adult son or daughter of the person.
  - A custodial parent of the person.
  - Any adult brother or sister of the person.
- In emergency room research settings, no surrogate consent may be utilized if there is a disagreement whether to consent among any available surrogates.
- If the potential research subject has questionable capacity, the investigator shall proceed with the standard consent process and document the subject's abilities to understand and express a reasoned choice. If there is lack of decisional capacity, the investigator shall inform the subject of the intent to obtain surrogate consent. If the subject expresses resistance, the subject shall be excluded from the research study. If there is no resistance expressed, the investigator will proceed to obtain surrogate consent. Subsequently, the investigator shall describe the consent process to the surrogate.
- A subject who regains the cognitive ability to consent must be re-consented using standard consenting procedures.

---

# **A Multi-Center Study on the Utility of Non-invasive Carboxyhemoglobin and Total Hemoglobin Measurement in Emergency Department Patients**

## **SUNE0002 version 3**

---

### HIPAA Waiver for Subject Screening

The screening of patients will require the investigators to access personal health information to identify prospective subjects without HIPAA authorization. The research could not be practicably carried out without this waiver of consent. The risk of harm from contacting the participants is greater than the risk of the study procedures. The research is of minimal risk and does not involve any procedures for which written consent is normally required outside the research setting. The participants' rights and welfare will not be adversely affected by waiving consent. This protected health information will not be inappropriately reused or disclosed to any other person or entity. To further safeguard all protected health information, the data will not be labeled with any personal identifying information, or with a code that this research team can link to personal identifying information. The data will not be stored with any protected health information identifiers.

### **5.5 Withdrawal of Subjects**

Informed consent discussions will explicitly include emphasis that neither patient enrollment nor patient withdrawal from the study will result in any alterations to the standard clinical care. Subjects may elect to withdraw at any time.

## **6 STUDY DEVICE**

Masimo Rad-67 pulse co-oximeter

Masimo DCI Mini Super sensors

### **6.1 Device Accountability**

#### **6.1.1 Receipt of Study Device**

Upon receipt of the of the study device supplies, an inventory must be performed and the device accountability log filled out and signed by the person accepting the shipment. It is important that the designated study staff counts and verifies that the shipment contains all the items noted in the shipment inventory. Any damaged or unusable study devices in a given shipment will be documented in the study files. The investigator must notify the study sponsor of any damaged or unusable study devices that were supplied to the investigator's site.

#### **6.1.2 Use of Study Device**

Use of devices and sensors will be documented on case report forms for each subject.

#### **6.1.3 Return or Destruction of Study Device**

At the completion of the study, there will be a final reconciliation of study devices and sensors shipped, devices/sensors used, and devices/sensors remaining. This reconciliation will be logged on the device accountability log. Any discrepancies noted will be investigated, resolved, and documented prior to return or destruction of unused study devices. Devices destroyed on site will only be upon written instruction from the sponsor and will be documented in the study files.

## **7 STUDY PROCEDURES**

Stage 1: After obtaining informed consent, from the patient (18 y.o. and over), legal guardian (<18 y.o.) with child assent or patient surrogate, as appropriate, the sensor will be placed as per sensor directions for use (DFU), and the SpCO and SpHb values recorded (this process takes less than 1 minute and is not associated with any pain or discomfort). Near-simultaneously (██████████), a █ ml vial of blood will be withdrawn from the patient's IV site for analysis. No new needle sticks will be performed. The study will not interfere with any aspects of patient care. The blood analysis for COHb will be performed immediately in the ED using a blood gas analyzer specifically obtained and properly calibrated for this study, by research personnel who will receive a standardized training program on its use. The patients will incur no additional cost and they will experience no delay in care or any prolongation of their stay in the ED stay related to this study. Hospital Laboratory Hemoglobin values, if measured as part of patient care, will be obtained from the patient's chart and

---

# A Multi-Center Study on the Utility of Non-invasive Carboxyhemoglobin and Total Hemoglobin Measurement in Emergency Department Patients

## SUNE0002 version 3

---

recorded on the case report forms (CRF). Demographic information, height, weight, gender, age, skin color, vital signs (heart rate, blood pressure, respiratory rate, pulse oximetry), presence or absence of jaundice, smoking history will be recorded on CRFs along with the values of SpCO, SpHb, COHb and hemoglobin concentration. If an abnormal COHb (>10%) value is observed, the measurement will be repeated using a Masimo FDA-cleared pulse CO-oximeter (e.g. Rad-57 and DCI sensor). If abnormal values are confirmed, the patient's clinician will be notified by research staff immediately. The clinician will independently determine any course of action related to patient care utilizing this information. CRFs will be kept within a locked filing cabinet in the Emergency Medicine Research Office which is locked. A de-identified data spread sheet will be created and kept on a storage device with encryption.

Stage 2: We will also approach patients with known CO exposure or who have anemia to enroll them in an arm of this study. Research staff will be notified of any patient presenting to the emergency department with suspected CO exposure or toxicity including patients with signs and symptoms of CO toxicity (headache, nausea, vomiting, rescued from fire, unexplained neurological deficits) or who have low hemoglobin values for any reason determined as part of their routine care. The treating provider will be notified if the patient has agreed to participate and if the clinician determines an IV is necessary, these patients will also be eligible for inclusion in the study.

Stage 3: In some cases of confirmed COP, patients will be asked to participate in an arm of the study where elimination pharmacokinetics of CO from the blood is determined. Serial, non-invasive measurements ( ) of SpCO, SpMeth, SpO2 and SpHb will be obtained from patients with SpCO or COHb concentration of or higher. Three additional ml. blood samples will be obtained from this selected group for COHb analysis during this hour after the first COHb sample for blood gas analysis. For children under the age of 8, the three additional samples will be no more than ml each. We will record the method and amount of O2 administered during the hour of treatment, so that we can analyze the effects of varying FiO2 on CO elimination kinetics.

For patients ultimately determined to have a CO poisoning or anemia diagnosis, the treating clinicians will be surveyed by the research personnel in real-time to determine if the clinicians thought screening impacted patient care for these patients (the short survey is included below).

At the end of study data analysis, if the clinical utility of the investigational device is demonstrated through this study, the data from the Stage 1 subjects will be unmasked. Study sponsor and/or the investigators will retrospectively analyze the data collected from these subjects to determine if any subjects had high CO readings. Such subjects will be contacted to inform that the Masimo device measured high levels of CO during their ED visit and to consult with their healthcare provider.

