#### 1.1 Background and Rationale

Carbon monoxide (CO) is the leading source of poisoning in the US and elsewhere. CO poisoning (COP) can cause severe disability and death. CO is released whenever there is combustion of fossil fuels including wood, oil, kerosene, etc. The diagnosis of COP is made when exposure to CO occurs and there are signs and symptoms consistent with toxicity. Exposure can be determined either with measurement of environmental CO levels or carboxyhemoglobin (COHb) concentrations in the blood. COP can cause headache, nausea, vomiting, dizziness, syncope, loss of consciousness, coma, focal neurological deficits, psychiatric manifestations and cardiac ischemia. Because CO is colorless, tasteless and has no odor, patients may not know if they have been exposed. Universal screening with a blood test is not feasible and not typically performed. Many of the signs and symptoms associated with COP are non-specific and may be attributed to other conditions if CO exposure is not considered. Patients could therefore be released from the hospital to return to an environment with CO potentiating toxicity, leading to death or severe disability. The use of environmental CO detectors has increased in public facilities and private homes in the US, but screening of emergency medicine subjects for CO exposure is not yet a standard practice. A device which estimates COHb concentrations non-invasively using a finger probe has been approved by the FDA and utilized in clinical care. This device passes 8 separate frequencies of light through the fingertip and measures absorbance at those frequencies during pulsatile blood flow, allowing estimation of pulse oximetry (Sp) hemoglobin species (Oxyhemoglobin: SpO2, total hemoglobin: SpHb, carboxyhemoglobin SpCO, and methemoglobin: SpMet). We have used this device at Rhode Island Hospital to screen patients who presented for any complaint and showed that 1-4/10,000 patients had unsuspected (both to the patient and clinician) COP. The sources of exposure were often faulty exhaust systems or dysfunctional appliances in the home. Other investigators have replicated these findings in Vermont (unpublished), Europe and Turkey. Studies which have evaluated the accuracy of the device when compared to blood COHb measurements have shown variable results. Taken together, these studies show that sensitivity of the device has utility for COP screening, but it does not have the accuracy to replace blood COHb.

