### SpCO:

1. Measure extent of agreement between SpCO and COHb determined by co-oximeter measurement of blood in the emergency department.
2. Determine diagnostic performance characteristics of SpCO (sensitivity, specificity, False Positive and False Negative) compared to gold standard of laboratory measurement of COHB in whole blood using a co-oximeter. We will define *a priori* a “true positive” of COHb  $\geq 7$  for COP.
  - a. We will also dichotomize smokers and non-smokers, and perform a post-hoc analysis to determine if the use of an alternate threshold for “true positive” based on smoking history is feasible.
3. Determine utility of SpCO for screening purposes by surveying the provider to determine the impact of screening test. Providers will be asked: Did the patient have a CO poisoning clinical diagnosis? Did SpCO screening lead to identification of occult toxicity?
4. Determination of elimination pharmacokinetics of CO in emergency department patients with CO toxicity as related to method of O2 administration (nasal cannula, non-rebreather mask, CPAP, or endotracheal intubation). Clinicians will administer O2 as dictated by patient care, the method and amount of O2 will be recorded. CO elimination will be evaluated as a function of FiO2.

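### Section 7 lets a pulse CO-oximeter reading decide whether a blood COHb above 10% reaches the treating clinician during the visit

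*Combined protocol and SAP*

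**What the plan says.** Section 7, Stage 1, has the study blood sample drawn close in time to the sensor readings, and "The blood analysis for COHb will be performed immediately in the ED". The alert rule has two steps. The trigger is: "If an abnormal COHb (>10%) value is observed, the measurement will be repeated using a Masimo FDA-cleared pulse CO-oximeter". The condition for passing the result on is: "If abnormal values are confirmed, the patient's clinician will be notified by research staff immediately". What counts as confirmation is not spelled out. The clinician then decides independently what to do.

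Two other places bear on how much weight each test carries. Section 2, SpCO item 2, compares SpCO with the "gold standard of laboratory measurement of COHB in whole blood using a co-oximeter". Section 1.1, on the existing FDA-approved finger-probe device, concludes that its sensitivity is useful for screening but that "it does not have the accuracy to replace blood COHb".

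The only later route to disclosure is at the end of section 7. After the final analysis, and only if the device is shown to be useful, Stage 1 subjects with high device readings are to be contacted.

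**The concern.** The order of authority is reversed. A blood result above 10% on the reference method is in the study team's hands within the visit, yet a reading from the less accurate method decides whether the clinician hears of it. A low pulse reading in a patient with a truly raised COHb is exactly the error that the reference test exists to expose. Here that error would also withhold the information.

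The harm is the one section 1.1 uses to justify the study: "Patients could therefore be released from the hospital to return to an environment with CO potentiating toxicity". It falls mainly on patients in whom nobody suspects exposure. Those enrolled because of known or suspected exposure are less affected, since their clinician is already alert to it.

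**Working it through.** The plan gives no figure for this point, so the check is mainly a comparison of rules.

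**Inputs**

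- Blood COHb is available during the visit (section 7, Stage 1).
- The trigger is COHb above 10%, repeated by pulse CO-oximeter, with notification only on confirmation (section 7, Stage 1).
- Blood co-oximetry is the reference (section 2, SpCO item 2).
- The existing pulse device is not accurate enough to replace it (section 1.1).
- Unsuspected poisoning is put at 1 to 4 per 10,000 (section 1.1) and 1 to 3 per 10,000 (section 5.1).
- Planned enrolment is 3000 subjects, about 1000 per site (section 5.1).

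**Step 1: apply the rule to a subject with blood COHb above 10%**

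| Reading of the trigger | Pulse result | Is notification required? |
|---|---|---|
| COHb, as printed | repeat confirms | Yes |
| COHb, as printed | repeat does not confirm | No stated rule |
| SpCO intended | first SpCO not above 10% | No stated rule |
| SpCO intended | first SpCO above 10%, repeat does not confirm | No stated rule |
| SpCO intended | first SpCO above 10%, repeat confirms | Yes, but for the pulse value; no rule for the blood value |

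On either reading, a blood COHb above 10% can go unreported.

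**Step 2: look for another rule that closes the gap**

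- Stage 2 provider notification (sections 5.4 and 7) concerns agreement to take part, not a result.
- Triage oximetry (section 5.4) is charted only where it is done, and it is not the study blood value.
- The end-of-study contact is conditional, comes after analysis, goes to the subject and concerns the device reading, with no numeric limit.
- The blinding in section 2 (SpHb primary objective 1) covers the analyzer's total hemoglobin. It gives no reason to hold back COHb.
- The Stage 3 entry level is not legible in the public text. The visible Stage 3 wording contains no reporting rule.

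Nothing in the visible text closes the gap.

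**Step 3: size**

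Subjects whose result is withheld under the printed rule = N × p × (1 − s). Here N = 3000, p is the share with blood COHb above 10%, and s is the share of those that the pulse repeat confirms. The documents give neither p nor s, so the product cannot be computed.

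The stated rates of unsuspected poisoning offer a rough scale:

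- Expected cases in 3000: 3000 × 1/10,000 = 0.3; × 3/10,000 = 0.9; × 4/10,000 = 1.2.
- Per site of 1000: 0.1, 0.3 and 0.4.
- Chance of at least one in the study, 1 − exp(−expected): 0.259, 0.593 and 0.699, so about 26% to 70%.

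These cover any COHb level and assume that the screening rates hold in the enrolled sample. Section 1.1 obtained its rate by screening with the pulse device, so patients whom that device missed are not counted. The figures give scale and are not a ceiling.

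**The case against.** **The sentence may mean SpCO.** A pulse device repeats a pulse measurement, not a blood assay. On that reading a cleared device checks an investigational one, and the complaint that a pulse value overrides a blood value falls away. This is a fair reading and the text should be clarified. It does not rescue the plan, because the blood COHb would then have no reporting rule at any level.

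**Silence is not prohibition.** That is true: nothing forbids research staff from telling the clinician. But a three-site protocol that makes confirmation the condition for notifying invites staff to wait for it.

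**Telling clinicians the blood value may contaminate the survey.** The survey asks "Did SpCO screening lead to identification of occult toxicity", and a disclosed blood value could make the diagnosis that SpCO is meant to be credited with. This stands in part. However, the protocol already accepts such influence for confirmed values, and recording what was disclosed makes it visible, though it does not remove it. The agreement and accuracy analyses use pairs obtained before any notification, so they are unaffected.

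**Two stronger readings are tempting, and the documents support neither.**

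A reader might infer that the alert limit contradicts the definition of "a “true positive” of COHb $\geq 7$ for COP", so that values of 7 to 10% must be reported. The two limits do different jobs. Seven is a classification cut-off, and SpCO item 2a plans to revisit it by smoking history. Section 1.1 requires exposure together with signs and symptoms for a diagnosis. The share of subjects at 7 to 10% is not given. If it were 1% to 5% (an assumption), alerts would number 3000 × 0.01 = 30 to 3000 × 0.05 = 150, many probably in smokers, for probably less than one unsuspected case. Reasonable people would differ on that trade.

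A reader might also infer that limiting the survey to diagnosed patients (section 7) prevents the study from counting undiagnosed subjects with COHb of 7 or more. It does not. COHb is on the case report form, and applying the limit requires knowing the final diagnosis, so the count follows by subtraction.

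**Conclusion.** The point holds for blood COHb above 10%. As printed, the rule lets the less accurate test block the reference result. If SpCO was intended, the visible rules never require the blood result to be passed on. The number of subjects affected is unknown and the expected safety yield is small, but the value is already in hand and a missed case could be severe.

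This rests on the visible text. A reporting rule in a removed or redacted part would change the conclusion. It does not depend on treating 7% as an action level, and the absence of a rule for 7 to 10% is not an error. Label: cheap improvement.

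**What to change.** Amend section 7, Stage 1, as follows:

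1. Notify the clinician immediately of any study blood COHb above 10%, on the blood value itself, while the patient is still in the ED.
2. Still take and record the repeat pulse reading, but do not make it a condition for notifying.
3. State whether the trigger is COHb, SpCO or both. If a high SpCO is a trigger, use the blood COHb already drawn as the confirmation.
4. Record on the case report form that the clinician was told and which value was given.

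The clinician continues to decide on care. The sponsor may also consider a lower alert limit for 7 to 10%, with smoking status supplied, as a clinical decision.

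The cost is a short amendment, with the signatures and IRB approval that section 12.2 requires, and a small addition to the case report form. The extra notifications are only those above 10% that the pulse repeat would not have confirmed, which should be few. Some influence of the blood value on the diagnosis and the survey remains.

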### SpHb :

#### Primary objectives

1. Determine diagnostic performance characteristics of SpHb for detecting anemia (Sensitivity, Specificity, False Positive and False Negative) compared to reference hemoglobin measurement by the hospital laboratory, based on WHO criteria for anemia. For comparison, total Hb determined by blood gas analyzer will also be measured and used only related to research. This value will be not recorded in the medical record and will be kept blinded to clinical care team. This will be completed if sufficient number of participants with anemia are enrolled during the study period. (If not, a separate study related to this objective will be designed)
2. Determine utility of SpHb for screening purposes
  - a. Establish threshold of SpHb that best predicts the clinical outcome of “acute treatment of anemia”, defined as: blood transfusion, admission to hospital for further workup of anemia, or admission to operating room

---

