# A Multi-Center Study on the Utility of Non-invasive Carboxyhemoglobin and Total Hemoglobin Measurement in Emergency Department Patients

## SUNE0002 version 3

---

- b. The threshold of SpHb will be determined by receiver operating curve analysis of the pooled results from the first set of 500 subjects for each institution.
- c. Validate the SpHb threshold that predicts the outcome of “acute treatment of anemia” using a second set of subjects of 500 subjects from each institution.

Secondary objectives:

1. Measure extent of agreement between SpHb and total Hb determined by central hospital laboratory. Total Hb determined by blood gas analyzer will also be compared to the central laboratory measurement.
2. Survey the provider to determine the impact of the screening test. Providers will be asked: Did SpHb screening expedite care of patients? Did SpHb screening identify occult anemia?

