### 5 SUBJECT SELECTION AND WITHDRAWAL

#### 5.1 Number of Subjects

At least 3000 subjects across three sites may be enrolled onto this study. We expect to enroll approximately 1000 subjects at each site. This sample size is based on previous experience that has have demonstrated: 1) Occult toxicity occurs in approximately 1-3/10,000 ED visits. 2) Higher numbers of CO, needed to determine extent of agreement between non-invasive and laboratory measurements, are infrequent.

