### 5.4 Study Timelines

Subject participation in this study is not expected to delay any care or prolong their stay in the ED. The study will be conducted approximately between October 1, 2016 and December 31, 2018. We anticipate enrolling an average of 10 patients a day.

**Subject Recruitment** Patients may be screened at triage with FDA approved oximeter devices as part of standard of care procedures. The results of this screening will be recorded in the chart if performed, by clinical staff as per routine procedure.

A convenience sample of patients aged 1 year and up presenting to the emergency department for any complaint and who have received or will receive a blood test for CBC or an IV catheter during their care (determined by their care provider independently) or will be approached by trained research staff for evaluation for enrollment in the study.

We will also approach patients with known CO exposure or who have anemia to enroll them in this study. The attending emergency physician will conduct usual clinical care; research staff will seek to obtain informed consent for this part of the study.

Research staff will also be notified of any patient presenting to the emergency department with suspected CO exposure (e.g. rescued from fire), toxicity or anemia, or patients with signs and symptoms of CO toxicity (unexplained headache, nausea, vomiting, dizziness or lightheadedness, syncope, neurological deficits, shortness of breath). The treating provider will be notified if the patient has agreed to participate. If the clinician determines an IV is necessary, these patients will also be eligible for inclusion in the study.

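### The SpHb threshold and validation sets name no recruitment route, so enrolling patients for a known low hemoglobin could understate specificity for acute treatment of anemia at triage; report pooled and by reason for approach.

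*Combined protocol and SAP*

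**What the plan says.** Section 2 gives the purpose as judging the clinical utility of triage screening. SpHb primary objective 2 seeks the SpHb threshold that best predicts acute treatment of anemia, defined as "blood transfusion, admission to hospital for further workup of anemia, or admission to operating room". The threshold is "determined by receiver operating curve analysis of the pooled results from the first set of 500 subjects for each institution" and is then validated "using a second set of subjects of 500 subjects from each institution". Neither sentence names a stage or a recruitment route.

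There are several routes in. Section 5.4 (Subject Recruitment) describes a convenience sample of ED patients with any complaint who have a CBC or an IV. It then adds: "We will also approach patients with known CO exposure or who have anemia to enroll them in this study". Section 7, Stage 2 repeats this with a different ending ("We will also approach patients with known CO exposure or who have anemia to enroll them in an arm of this study"), extends it to patients with suspected CO exposure "or who have low hemoglobin values for any reason determined as part of their routine care", and says that "these patients will also be eligible for inclusion in the study" if the clinician judges an IV necessary.

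On numbers, Section 5.1 says "At least 3000 subjects across three sites may be enrolled onto this study", with about 1000 expected per site. The available text gives Stage 2 no size, share, hemoglobin cut-off or SpHb analysis of its own.

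**The concern.** The outcome is acute treatment, not low hemoglobin itself. A patient approached because of a low hemoglobin who is then not transfused, admitted for anemia workup or taken to the operating room is a non-event with a low SpHb, and so a likely false positive. If such patients are more common in the analysis set than among ED arrivals, specificity at any useful threshold falls below what triage would see. Sensitivity may move the other way, because treated patients with an already known low hemoglobin are the easy ones to detect.

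The two-set design does not protect against this. If both sets of 500 per site carry a similar mix, validation agrees with derivation and both are off. If the mix changes between the sequential sets, validation performance moves for case-mix reasons alone and could be mistaken for a threshold that fails or improves. Without the reason for approach, a reader cannot tell which has happened.

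**Working it through.** **1. The plan's own count.** 3 sites × (500 + 500) = 3000, which matches Section 5.1. If enrolment stops near 3000, everyone enrolled falls in one of the two sets, including subjects approached for low hemoglobin. But 3000 is a minimum, so the match does not prove it.

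**2. Direction.** At a fixed threshold,

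pooled specificity = (1 − w) × specificity in other subjects + w × specificity in the low-Hb route,

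where w is the low-Hb route's share of subjects without the outcome. With assumed specificities of 0.90 and 0.40:
- w = 10%: 0.90 × 0.90 + 0.10 × 0.40 = 0.85
- w = 20%: 0.80 × 0.90 + 0.20 × 0.40 = 0.80

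For comparison, the sampling half-width at 0.90 with 1500 non-events is 1.96 × √(0.90 × 0.10 / 1500) = 0.015. If everyone on the low-Hb route were treated, w would be 0 and specificity would not change.

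**3. Size under an assumed model.** None of these inputs is in the documents:
- ED hemoglobin: mean 13, SD 2 g/dL. SpHb error: SD 1.2.
- Probability of treatment: logistic in hemoglobin, midpoint 8, 9 or 10 g/dL, slope 1.0, 1.5 or 2.5 per g/dL.
- Low-Hb route: Hb below 10, 11 or 12.
- Threshold: maximum Youden index in the pooled set (0.1 g/dL grid), then applied to the pooled set and to unselected arrivals.

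| Low-Hb route, share of the set | Pooled specificity too low by (points) |
|---|---|
| 10% | 2 to 6 |
| 20% | 4 to 12 (4 to 7 if Hb below 12) |
| 40% | 7 to 24 |

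Example (20%, midpoint 8, slope 1.5, Hb below 12): sensitivity/specificity 83.7/80.4% pooled against 83.0/86.0% unselected. Few subjects have the outcome here, so w is close to 0.20. The identity in step 2 then implies a low-Hb-route specificity of about (80.4 − 0.80 × 86.0) / 0.20 = 58%.

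**4. CO-route subjects.** Stage 2 also takes patients with CO exposure, who have no reason to have low hemoglobin. If half of a 20% Stage 2 is low-Hb, the relevant share is 0.5 × 20% = 10%, and the gap is 2 to 6 points. If a quarter is, the share is 5% and the gap is 1 to 3.

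**5. Sensitivity.** If treatment depends on hemoglobin alone, pooled sensitivity at a 20% share is 0 to 17 points too high. Admission to the operating room can occur at normal hemoglobin. With an assumed 2% event rate unrelated to hemoglobin, the gap becomes about 5 to 31 points. The result depends too much on the assumption to be quoted as a size.

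**6. Sequential sets** (1500 + 1500, midpoint 8, slope 1.5, Hb below 12), mean specificity:

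| Low-Hb share, first/second set | Derivation | Validation, pooled | Validation, without low-Hb route |
|---|---|---|---|
| 20% / 20% | 80.8% | 80.6% | 86.0% |
| 10% / 30% | 82.2% | 76.4% | 84.9% |

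**7. The opposite bias.** Suppose half of arrivals with Hb below 12 are labelled to the low-Hb route although the convenience sample would have reached them anyway (15% of the set, no enrichment). Then the pooled set is right and the estimate without that route is 4 to 7 points too high. With both effects (20% share, half diverted), pooled specificity is 1 to 2 points too low and the other estimate 4 to 7 too high. Over 162 scenarios combining the two effects, the all-arrivals value lay between the two estimates in 153. In the other 9, both were too high.

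**The case against.** **Inclusion is not established.** A reader might infer that subjects approached for low hemoglobin are certainly in the 500 + 500 and that the planned specificity is therefore biased. The documents do not support that. Section 7 speaks of an arm and refers to Stage 1 subjects as a group, and Section 5.1 sets a minimum, so Stage 2 could be handled apart or on top. This objection stands, and the point is conditional for that reason. What remains is that two analysts could build different sets from the same text.

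**Stage 1 is not the correct answer either.** It is tempting to exclude Stage 2 and rest the triage conclusion on the remainder. Step 7 shows why not. A low hemoglobin found in routine care implies a routine blood test, and patients having a CBC are already in the convenience-sample pool, so diversion is plausible. Nothing in the documents shows which effect dominates. Excluding all of Stage 2 would also remove CO-route subjects, who do not cause the problem. The useful split is by reason for approach.

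**The 4 to 12 points are not a figure for Stage 2 as a whole.** They apply to the share approached for low hemoglobin, and the documents do not give the split.

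**Consequence.** The plan sets no specificity target that the bias could cross, and Section 9.4 leaves the CRF list open, so the needed field may already exist. Both points are fair, and they limit the seriousness.

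**Conclusion.** The point holds in conditional form, for SpHb primary objective 2. If subjects approached for a known low hemoglobin are inside the sets, are over-represented relative to ED arrivals, and are not all acutely treated, pooled specificity at a given threshold is understated for triage use. Sensitivity may be overstated by an amount that cannot be reliably sized.

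The true size is unknown. The specificity ranges above rest wholly on the assumed hemoglobin distribution, device error and treatment model, but over most of them the bias exceeds a sampling half-width of about 1.5 points.

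A reader might extend this to SpHb primary objective 1, detection of anemia. There, specificity is unaffected provided that those approached for anemia are truly anemic by the criterion used. Section 5.4 can be read as including suspected anemia, and Section 7 does not tie low hemoglobin to the WHO criterion, so even that is not guaranteed.

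This is a cheap improvement, not a defect that invalidates the analysis.

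**What to change.** In Section 2, with a matching CRF entry:

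- (a) State whether subjects approached for known low hemoglobin or anemia are inside or on top of the 500 + 500 per site.
- (b) Record at enrolment the reason for approach (routine convenience sample, known low hemoglobin or anemia, CO exposure) and the stage. It may not be recoverable later.
- (c) Fix one threshold from the derivation set. Report its validation sensitivity and specificity pooled and by reason for approach (low-Hb route against all others), with the low-Hb-route share in each set.
- (d) Do not rest triage statements on either estimate alone. Pooled specificity is too low if the low-Hb route is enriched; the estimate without it is too high if patients who would have been approached anyway are labelled to it. Show both, and state that they do not always bracket the true value.

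**Cost.** One or two CRF fields and some analysis wording; no added blood or subjects. The downside is imprecise sensitivity without the low-Hb route. At a 20% share and slope 1.5, the model leaves about 20 events per set with midpoint 8 (16/20, exact 95% CI 56% to 94%) and about 118 with midpoint 10 (93/118, 70% to 86%), so the pooled estimate stays alongside. Specificity without that route remains precise, to about ±2 points on 1080 to 1180 non-events. That group is still a convenience sample of patients with a CBC or an IV, so it only approximates triage.
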